## 7.7 Descriptive Statistics

General descriptive statistics for quantitative variables will include the n (the number of non-missing values), the mean, the standard deviation (SD), the median, the minimum (min) and the maximum values (max).

For categorical variables, the number (n) and percentage (%) of subjects with a specific level of the variable will be presented. The number of missing values will be displayed as a "Missing" category, where appropriate. Unless otherwise specified, the denominator for each percentage will be the number of non-missing observations within the analysis set and treatment group.

## 7.8 Definitions

### 7.8.1 Baseline

Baseline is defined as the last non-missing value available before the first study drug administration.

### 7.8.2 Date of First and Last Randomized Study Medication Intake

The date of first randomized study medication intake is the earliest date of randomized study medication intake considering the eCRF data, corresponding to the date part of the variable RFXSTDTC in the study data tabulation model (SDTM) dataset DM.

The date of last randomized study medication intake is the one recorded in the Treatment Termination form of the eCRF, corresponding to the date part of the variable RFXENDTC in the SDTM dataset DM.

### 7.8.3 Study Day

If not otherwise specified, all assessment days will be related to the first day of study drug administration (CUSA-081, placebo or alteplase).

The first day of study medication administration is referred to as Day 1. Day -1 is the day that precedes Day 1.

- If the date of the assessment is on or after the first study drug administration date, then

Study Day = (date of assessment – first study drug administration date) + 1.

- If the date of the assessment is prior to the first study drug administration date, then  
Study Day = (date of assessment – first study drug administration date).

### 7.8.4 Visit dates

For each visit, the variable SVSTDTC (minimum start date for each of the subject's assessments performed during a specific visit) in the SDTM SV dataset will be considered as the visit date in all the algorithms and the listings.

--TPT variable defined in each relevant SDTM will be used as the timepoint in all the algorithms and the listings.

### 7.8.5 Duration of Adverse Events or Medications

The duration of an AE or medication will be calculated as follows:

- End date – Start date + 1 (when both dates are completely known);
- Date of study completion/discontinuation – Start date + 1 (when the start date is fully known but the AE or medication still ongoing at the end of the trial): in this case the duration will be presented as ">x" days in the listing rather than "x" days;

- Missing (when the start date is incomplete or unknown, or when the AE or medication ended but with an incomplete or unknown end date, or when the start date is greater than date of study completion/discontinuation).

## 7.9 Diary Data

Not applicable. Diary data are not collected in this study.

## 7.10 Data Re-allocation

In general, for by-visit (or timepoint) summaries, data recorded at the nominal visit (or nominal timepoint) will be presented. Data collected at unscheduled time points will be reviewed at the Data Review Meeting prior to database lock. Any re-allocation of unscheduled data will be described and justified in the Data Review Report, which will be finalized prior to database lock. In any case, listings will include scheduled, unscheduled and early discontinuation data.

## 7.11 Exclusion of Data from the Statistical Analyses

### 7.11.1 Exclusion of Data from All Statistical Analyses

All data collected in the database will be used in all statistical analyses.

### 7.11.2 Exclusion of Data from Per-Protocol Analyses

In case of important protocol deviation (e.g., wrong inclusions, incomplete dosing, non-permitted concomitant medications), the subject will be excluded from the PP Set and therefore from all PP analyses.

In case of important protocol deviation impacting specific datapoint, only the specific datapoint will be excluded from the PP analyses.

Protocol deviations will be reviewed during the DRM. Important protocol deviations leading to the exclusion of the subject from the PP analysis, or to the exclusion of isolated data from the PP analysis will be agreed by the study team during the Data Review Meeting and documented in the Data Review Report prior to database lock and unblinding.

## 7.12 Listings

All data collected in the eCRF will be presented in the individual listings. All listings will be presented for the ITT Set, unless specified otherwise.

## 7.13 Coding

Medical and surgical history, concomitant diseases, procedures and adverse events will be coded according to Medical Dictionary for Regulatory Activities (MedDRA) version 22.0 or higher.

Medications will be coded using the World Health Organization Drug Dictionary (WHO-DD) version March 2019 or later.

## 8 Study Population

### 8.1 Disposition of Subjects and Discontinuations

#### 8.1.1 Disposition of Subjects

The number of subjects screened, the number screen failures and the reasons for screen failure will be presented (overall) based on Enrolled Set.

The number of subjects screened, randomized and completed will be presented by country and by site using ITT Set.

The number of subjects who performed each study visit will be summarized for the ITT Set.

#### 8.1.2 Discontinuation from the Treatment and the Study

The number of subjects who completed the treatment, withdrew from the treatment, the reasons for withdrawal from the treatment, completed the study, withdrew from the study and the reasons for withdrawal from the study will be presented by treatment group using the ITT Set.

The number of subjects who discontinued the treatment and the study will be also presented by country and by site using ITT Set.

An individual subject listing will be provided for the disposition data.

#### 8.1.3 Protocol Deviations and Analysis Sets

Deviations will be classified according to the categories defined in the Data Review Report.

Important protocol deviations affecting the efficacy analyses will be summarized by treatment group using the FAS. The ones excluding from PPS will be also summarized.

The number of subjects included in each of the FAS, Safety and PP Sets will be summarized for each treatment group and overall using the ITT Set.

### 8.2 Demographic and Baseline Characteristics

No formal comparison between treatment groups on demographic and baseline characteristics will be performed.

#### 8.2.1 Demographic Characteristics

Demographic and baseline characteristics will be summarized by treatment arm and overall using descriptive statistics for the FAS. These will include age, age category, gender, race, ethnicity, height, weight at baseline, body mass index (BMI) at baseline, systolic blood pressure (SBP) at baseline, diastolic blood pressure (DBP) at baseline, heart rate (HR) at baseline and urine pregnancy test results. Separate summaries for demographic and baseline characteristics will also be produced using the Safety, ITT and PP Sets.

**Notes:**

- BMI will be calculated as: weight at the visit (kg) / height at Visit 1 (m^2).
- Age categories are: <18 years, ≥18-<65 years, ≥65-<85 years and ≥85 years. All categories must be reported even if there are no subjects under a particular category.

An individual subject listing will be provided for demographic and baseline characteristics data.

**8.2.2 CVAD History**

Time between Screening CVAD assessment and first drug administration (hours), CVAD type, CVAD lumen, number of lumens, indications for CVAD insertion, duration of CVAD dysfunctional (hours) and when and by whom the CVAD was identified as dysfunctional (Patient/caregiver identified, Healthcare provider not at study site, Healthcare provider at study site) recorded at Screening Visit will be presented by treatment group and overall using the FAS. Summaries will be repeated using the Safety, ITT and PP Sets.

**Notes:**

- Time between Screening CVAD assessment and first drug administration (hours) will be calculated as: Date/Time of first study drug administration – Date/Time of Screening CVAD assessment.

In addition, CVAD history data will be presented in an individual listing.

**8.3 Medical History and Concomitant Diseases**

Medical/surgical history and concomitant diseases will be summarized by System Organ Class (SOC) and Preferred Term (PT), by treatment group and overall. Summaries will be produced using the Safety Set.

**Notes:**

- Medical/surgical history is defined as conditions in the medical/surgical history and concomitant diseases eCRF form which are not ongoing at Screening Visit (even if end date is missing);
- Concomitant diseases are defined as conditions in the medical/surgical history and concomitant diseases eCRF form which are ongoing at Screening Visit (“ongoing” tickbox is ticked or end date > Screening Visit date).

In addition, medical, surgical and concomitant diseases data will be listed.

**8.4 Medications**

Prior medications, medications maintained during the randomized treatment period, and concomitant medications will be summarized by treatment group and overall (except for concomitant medications) for the Safety Set through frequency distributions and percentages by Anatomical Main Group [1st level of the Anatomical Therapeutic Chemical (ATC) classification], Therapeutic Subgroup (2nd level of the ATC classification), Chemical Subgroup (4th level of the ATC classification) and Preferred Name. In addition, maintained

medications and concomitant medications will be summarized using the FAS. Post-treatment medications will only be presented in a listing.

The medications will be classified according to the following rules (See also Section 7.3):

- Prior medication: start date/time < date/time of first randomized study medication intake and stop date  $\leq$  date/time of first randomized study medication intake;
- Medication maintained during the randomized treatment period: start date/time < date/time of first randomized study medication intake and stop date/time > date/time of first randomized study medication intake or ongoing;
- Concomitant medication: date/time of first randomized study medication intake  $\leq$  start date/time < date/time of last randomized study medication intake;
- Post-treatment medication: date/time of last randomized study medication intake  $\leq$  start date/time.

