## 2 Study Design

This is a phase 3 multinational, multicenter, prospective, randomized, double-blind, parallel-group, active and placebo-controlled study examining the effect of instillations of CUSA-081 versus placebo or alteplase in subjects with dysfunctional non-hemodialysis CVADs. Restoration of CVAD function is defined as follows: the ability to both withdraw at least 3 mL of blood and infuse 5 mL of saline.

Subjects will be screened according to the Study Inclusion and Exclusion criteria and will be candidates for randomization if all eligibility criteria are met.

A minimum of 841 subjects, within approximately 100 sites, will be randomized, in a 9:1:6 ratio of CUSA-081:Placebo:alteplase in order to achieve a minimum of 800 subjects completing the study:

Treatment Arm A (CUSA-081 [reteplase])	473 subjects
Treatment Arm B (Placebo)	53 subjects
Treatment Arm C (alteplase)	315 subjects

A total of 2-3 visits will be performed during the study, as follows (refer to the Study Treatment Schema in Figure 1 for more details):

[figure not shown]
- Screening (Baseline Visit) (Day 0 or Day 1).
- Treatment Visit 1 (V1) (Day 1):
  - Subjects will receive the first instillation of study drug (CUSA-081, placebo or alteplase) into the catheter via the single lumen designated for this study.
  - If patency is not restored after 90 minutes following the first instillation, a second dose of study drug (same drug as at first instillation) will be administered.
- Follow-up Visit 2 (V2) (Day 30 ± 2 days) (can be performed by telephone).

An extra visit could be performed as Screening (Baseline Visit) for logistical reasons. Day 1 must be the following calendar day (for example, Monday and Tuesday; not Friday and Monday). Informed consent will be signed during this visit.

Safety will be monitored throughout the study.

The end of the trial is defined as the last follow-up contact of the last subject to receive study drug in the trial.

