-  Subjects who are unable to be reached for follow-up assessment after discontinuing study drug will be categorized as lost to follow up from the study.
-  The Day 30 ( $\pm 2$  days) follow-up assessment will occur via phone or may occur in person if the subject has a scheduled clinic visit. The follow-up period is calculated from the date of the randomization/treatment day.
-  A urine pregnancy test is required for all females of childbearing potential. Women in natural or surgical post-menopause do not need to be tested for pregnancy.
-  Only concomitant medications and/or procedures ongoing at the time of consent, or stopped within 30 days prior to informed consent, and only new concomitant medications and/or procedures related to spontaneously reported SAEs/AESIs will be collected after randomization.
-  Note that all catheter assessments are based on the dwell time from the time of study drug instillation (i.e., from "0 min"; NOT from the time of the prior assessment). All efforts should be made to conduct the assessment at the required time point. The window of  $\pm 5$  minutes is also from the time of study drug instillation and not time of the prior assessment. Assessments of catheter dysfunction are described in Sections 7.1.1 and 7.2.3 of the protocol. In the event a 2nd dose of study drug is needed, it should be administered within 15 min of withdrawal of the 1st dose from the CVAD.
-  Once CVAD function has been restored (i.e. the ability to both withdraw at least 3 mL of blood and infuse 5 mL of saline solution), the subject will be deemed a Treatment Success and will exit the treatment algorithm (Figure 1). Therefore, subsequent dosing and catheter function checks will not be performed during V1. At 180 minutes, or in the case of Early Withdrawal, if treatment success is not achieved, any subsequently administered standard of care and related outcome will be documented.

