## 8.5 Procedures

Prior procedures, procedures maintained during the randomized treatment period and concomitant procedures will be summarized by treatment group for the Safety Set through frequency distributions and percentages by SOC and PT. Post-treatment procedures will only be presented in a listing.

The procedures will be classified according to the following rules (See also Section 7.3):

- Prior procedure: start date/time < date/time of first randomized study medication intake and stop date  $\leq$  date/time of first randomized study medication intake;
- Procedure maintained during the randomized treatment period: start date/time < date/time of first randomized study medication intake and stop date/time > date/time of first randomized study medication intake or ongoing;
- Concomitant procedure: date/time of first randomized study medication intake  $\leq$  start date/time < date/time of last randomized study medication intake;
- Post-treatment procedure: date/time of last randomized study medication intake  $\leq$  start date/time.

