### 10.2 Adverse Events

An AE will be classified as follow (See also Section 7.3):

- Pre-treatment AE: if it starts before the first study drug intake (AE onset date/time < date/time of first study drug intake);
- Treatment emergent AE (TEAE): if it starts on or after the first dose of study drug intake up to the end of the treatment period (date/time of first study drug intake ≤ AE onset date/time ≤ end date/time of the treatment period);
- Post-treatment AE: if the onset date is after the end of the treatment period (AE onset date/time > end date/time of the treatment period).

The treatment period is defined as the period between first study drug administration and the following end:

- For subjects who completed the treatment period without achieving treatment success, the end of the treatment period will be the date/time of the 180-minutes CVAD assessment;
- For subjects who achieving treatment success, the end of the treatment period will be the date/time of the CVAD assessment where patency is achieved;
- For subjects who discontinued the treatment due to AE or death, the end of the treatment period will be the start date/time of the relevant event and the event will be considered as treatment emergent;
- For subjects who discontinued the treatment due to other reasons, the end of the treatment period will be the date/time the last CVAD assessment performed.

An ADR is an AE related to study medication. A serious ADR is a SAE related to study medication.

A severe AE is an AE with severe intensity. Refer to Section 7.3 for missing severity.

An AE leading to discontinuation is an AE with action taken with study drug equal to “Drug Permanently Withdrawn”.

An AE leading to death is an AE with outcome equal to “Fatal”.

Two AEs with the same PT and classified in the same category (pre-treatment AE, TEAE or post-treatment AE) will be considered as two different events when calculating the “number of events” in the tables.

Pre-treatment AEs, TEAEs and post-treatment AEs will be presented separately. Pre-treatment AEs will be presented in the listings only.

A summary table displaying the number and the percentage of subjects experiencing at least one TEAE, serious TEAEs, ADRs/drug-related TEAE, serious ADRs, severe TEAEs, TEAEs leading to study drug discontinuation, TEAE of special interest (See Section 10.2.1) and TEAEs leading to death, as well as the number of events, will be presented by actual treatment group.

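### SAP 8.4 and 8.5 close the concomitant window at the last study drug intake, which leaves it empty for one-syringe subjects and at odds with the SAP 10.2 treatment period

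*SAP*

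**What the plan says.** SAP 8.4 has four medication categories. Two matter here:

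- "Concomitant medication: date/time of first randomized study medication intake" or later, and strictly before the last intake.
- "Post-treatment medication: date/time of last randomized study medication intake" or later.

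SAP 8.5 repeats the rule for procedures, beginning "Concomitant procedure: date/time of first randomized study medication intake". The prior and maintained categories depend on the first intake only.

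The label decides what is tabulated. Concomitant items are summarised by treatment group in Tables 14.1.8.1 (procedures, Safety Set), 14.1.11.1 (medications, FAS) and 14.1.11.2 (medications, Safety Set). By contrast, "Post-treatment medications will only be presented in a listing"; procedures are treated likewise.

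On last intake, SAP 7.8.2 says: "The date of last randomized study medication intake is the one recorded in the Treatment Termination form of the eCRF". It links this to the date part of an SDTM variable and does not say which clock time applies.

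SAP 2 makes the second syringe conditional: "If patency is not restored after 90 minutes following the first instillation, a second dose of study drug" is given. Table 1 adds that "it should be administered within 15 min of withdrawal of the 1st dose from the CVAD".

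SAP 10.2 uses a different period for adverse events. For subjects with treatment success, "the end of the treatment period will be the date/time of the CVAD assessment where patency is achieved". For subjects who complete without success it is the 180-minute assessment.

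**The concern.** Study drug acts while it dwells in the catheter, for up to 90 minutes per syringe. A concomitant window that stops when a syringe is instilled leaves that dwell out. For a one-syringe subject it leaves out the whole treatment period.

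Two consequences follow. First, the concomitant tables can show nothing for one-syringe subjects, whatever was recorded, and a reader could take the blank as evidence that nothing was started during treatment. Second, the SAP would use two incompatible treatment periods in one report. Suppose an adverse event starts 20 minutes after a single instillation, a medication for it starts at 25 minutes, and patency is found at 30 minutes. Under SAP 10.2 the event is treatment-emergent. Under SAP 8.4 the medication is post-treatment and is absent from the table.

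**Working it through.** The plan states no figure for this window, so none can be reproduced. The success rates come from the sample size section, and the 75% rate can be checked there: SE = √(0.75×0.25/450 + 0.75×0.25/300) = 0.0323, and Φ(0.10/0.0323 − 1.96) = 87.3%, against the stated 87%.

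**Inputs**
- Success at 90 minutes: 75% in both active arms, about 20% on placebo (SAP 5).
- Planned subjects: 473 CUSA-081, 53 placebo, 315 alteplase, 841 in all (SAP 2).
- Time from first to second instillation: 90 minutes plus up to 15, so 90 to 105 nominally. The ±5-minute assessment window widens this to 85 to 110.
- Assumption: the time of last intake is the time of the last instillation.

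**Window length** = last intake − first intake.
- One syringe: first = last = t. No start time s satisfies t ≤ s < t, so the window is empty.
- Two syringes: 90 to 105 minutes, closing as the second dwell begins.

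**By arm at planning rates**

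| Arm | One-syringe subjects | Mean window (min) |
|---|---|---|
| CUSA-081 | 473 × 0.75 = 354.8 | 0.25 × 90 to 105 = 22.5 to 26.3 |
| Placebo | 53 × 0.20 = 10.6 | 0.80 × 90 to 105 = 72 to 84 |
| Alteplase | 315 × 0.75 = 236.3 | 22.5 to 26.3 |

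Empty windows: 354.75 + 10.6 + 236.25 = 601.6, and 601.6/841 = 71.5%.

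**Range of that share**
- CUSA-081 at 55% (placebo 20% plus the 35-point difference): 507.0/841 = 60.3%.
- CUSA-081 at 85% (75% plus the 10-point difference): 648.9/841 = 77.2%.
- Alteplase at the interpolated historical 67.3%, placebo at the pooled 19%, CUSA-081 at 75%: 576.8/841 = 68.6%.

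**Date-only reading.** All dosing takes place on Day 1, so the first and last dates are equal and the window is empty for every subject in every arm.

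**Window under the SAP 10.2 period.** It is non-empty for any subject with a post-dose assessment who did not stop treatment at an event, at about 30 minutes or more. The split of success times is unknown, so only bounds on the mean can be given, ignoring early discontinuation:
- Active arms: 0.75×30 + 0.25×120 = 52.5 to 0.75×90 + 0.25×195 = 116.3 minutes.
- Placebo: 0.20×30 + 0.80×120 = 102 to 0.20×90 + 0.80×195 = 174 minutes.

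The upper bounds use 180 minutes plus the 15 allowed before the second dose.

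**The case against.** The strongest objection is that little depends on this label, and most of that stands.

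- **Few entries.** After randomization only new medications and procedures related to spontaneously reported SAEs or AESIs are collected (footnote 6 of the study schedule). Items already ongoing at dosing are maintained and are tabulated. Standard-of-care treatment after failure has its own Listing 16.2.6.2.
- **Nothing is lost from the listings.** Listings 16.2.4.5 and 16.2.4.6 show procedures and medications with start and end times and category, including post-treatment.
- **The form is not available.** The eCRF's Treatment Termination form might record the end of dwell as last intake, in which case the window would work. The SAP does not say so, and its word is intake. The worst-case rule for incomplete times in SAP 7.3 puts concomitant first, but only among categories the data allow. With known dosing times and one syringe, that category is never possible.

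A reader might infer that a barred fibrinolytic given in another lumen during a dwell would escape notice and so affect the Per-Protocol Set that decides non-inferiority. The documents do not support this. Per-protocol exclusions are agreed at the blinded Data Review Meeting (SAP 7.11.2), not taken from these tables. The bar on other lumens is set for 0 to 180 minutes in protocol 5.2, independently of SAP 8.4. The bar on intravenous agents in the 24 hours before dosing concerns prior and maintained items, which are unaffected. On the collection rule above, such a drug would be recorded as a concomitant medication only if linked to an SAE or AESI.

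A reader might also infer that efficacy distorts a between-arm comparison and makes the tables wrong. They are frequency tables with no test or contrast specified. At 75% in both active arms, CUSA-081 and alteplase have equal expected windows; the expected difference, about 3.2-fold (72/22.5), is against placebo only.

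**Conclusion.** The point holds as a minor reporting defect. On a date/time reading with last intake as the last instillation, the concomitant category is impossible for one-syringe subjects: about 71.5% of planned subjects at planning rates, 60% to 77% across the scenarios shown. For two-syringe subjects it omits the second dwell. On a date-only reading it is impossible for everyone. Either way it contradicts the SAP 10.2 treatment period.

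The reach is Tables 14.1.8.1, 14.1.11.1 and 14.1.11.2. No efficacy, per-protocol or adverse event analysis uses the classification.

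The counts use planned arm sizes. SAP 12 says the study was stopped early, and the documents do not give the numbers enrolled. The within-arm shares depend on the success rates, not on the arm sizes.

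**What to change.** In SAP 8.4 and 8.5, replace the time of last intake with the end of the treatment period as defined in SAP 10.2:

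- Concomitant: first intake ≤ start ≤ end of treatment period.
- Post-treatment: start after the end of the treatment period.

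Add two statements:

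1. The window still varies with response, because the SAP 10.2 period ends at success. The change removes the empty interval and the contradiction, not the dependence on response.
2. For subjects who stop treatment because of an adverse event, the SAP 10.2 period ends at the onset of that event. Medication started afterwards for it would still be post-treatment unless the SAP explicitly assigns it to concomitant.

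If last intake is kept instead, SAP 7.8.2 should define its clock time, and SAP 8.4 and 8.5 should explain the difference from 10.2.

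The cost is a few lines of SAP text and one derivation. No new data are needed, and SAP 12 describes database lock and unblinding as still to come.
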